4.5.17 NON-INVASIVE TEAR FILM BREAK UP TIME (NITBUT) (KEELER TEARSCOPE)

The participant will be seated at a slit lamp and a diffuse white light will be shone onto the participant's eye without a grid insert. The Keeler Tearscope is a hand-held device with projects a diffuse white light onto the surface of the eye to allow the investigator to better see the lipid layer

of the tear film while the participant is sitting behind the slit lamp. This device is not computerized and does not generate data. The timer on the instrument will be used to measure the non-invasive break-up time. The non-invasive break-up time will be recorded as the time taken after a blink until the appearance of the first dark spot.⁷ Three measurements will be taken from each eye and the average value will be calculated for each eye.

4.5.18 LIPID LAYER THICKNESS (KEELER TEARSCOPE)

The participant will be seated at a slit lamp and a diffuse white light will be shone onto the participant's eye. Lipid layer thickness will be graded according to the interference pattern observed based on Guillon and Guillon's classification system⁷ (open meshwork, closed meshwork, wave, amorphous, colour fringe, and other).

4.5.19 LIPID LAYER THICKNESS (TEARSCIENCE LIPIVIEW II)

The participant will be seated at the LipiView II instrument which will image and compute the lipid layer thickness (average, minimum, maximum) of the tear film. Prior to the commencement of this test, no history of seizures or discomfort with rapidly blinking lights will be confirmed.

5 MONITORING PROTOCOL ADHERENCE

Guidelines to be included on adherence to visit windows and windows around other data collection points (i.e. subjective ratings) will be monitored by CORE. Deviations from the windows described in the protocol will be reported in the study report. Major protocol deviations will be reported to the University of Waterloo's Office of Research Ethics (ORE) within 7 days of becoming aware of them (as per ORE's guidelines).

6 POTENTIAL RISKS AND BENEFITS TO HUMAN PARTICIPANTS

This is a minimal risk study because of the use of marketed products and standard optometric assessments with two investigational, non-invasive devices (the prototype evaporimeter and the modified swimming goggles used to measure volume).

Contact lenses in this study will be worn on a daily wear basis, for approximately 6 to 7 hours. Adverse events and/or complications in daily wear of soft contact lenses can occur (eg: inflammation and infection). When contact lenses are worn on a daily wear basis there is a small risk of an adverse event compared to not wearing contact lenses. When contact lenses are worn on an extended wear basis, there is a significantly increased risk of an adverse reaction compared with wearing contact lenses on a daily wear basis.

Additionally, it is possible that participants may experience temporary discomfort associated with the study procedures (saline)/products/devices including: burning and stinging, blurred vision, sandiness or grittiness, light sensitivity, dryness, itching, crusty eyes and foreign body sensation.

A dye (fluorescein) normally used for eye exams is being used in this study. Although rare, it is possible that participants may have an allergic reaction to the dye. This could cause discomfort to their eye.

Routine clinical procedures including visual acuity, anterior ocular health assessment, and contact lens fitting will be used.

One clinical procedure (evaporimetry) will be conducted with an investigational device consisting of a pair of modified swimming goggles containing a temperature and humidity sensor embedded in each lens of the goggle. This procedure poses minimal risk to the participants as the device does not touch the eye and the portion of the goggle which will come in contact with the skin surrounding the eye will be cleaned with alcohol wipes between each use. Participants may experience temporary discomfort associated with petroleum jelly including; burning, stinging, irritation, blurred vision, and foreign body sensation.

One clinical procedure (measurement of volume inside the goggle) will be conducted with an investigational device consisting of a pair of modified swimming goggles containing small hole inserted into the top of each lens. This procedure poses minimal risk to the participants as the device does not touch the eye and the portion of the goggle which will come in contact with the skin surrounding the eye will be cleaned with alcohol wipes between each use. Commercially available saline designed for use with the eyes will be inserted into the goggle. Participants may experience temporary discomfort associated with saline including; burning, stinging, irritation, blurred vision, and foreign body sensation.

One of the instruments in this study uses rapidly blinking lights to image the tear film. Participants will be asked to inform the investigator if they have a history of discomfort and seizures due to rapidly blinking lights. Participants may experience temporary discomfort including: blurred vision and light sensitivity.

Participants may not benefit directly from taking part in this study. Information from this study may help researchers come up with new devices to help others in the future. This study may help CORE to better understand the performance of the products being used in this study.

7 ADVERSE EVENTS

See CORE SOP012_v02 for a description of all adverse events, including management and reporting.

A number of conditions may result in temporary suspension until resolution. These include corneal infiltrates, corneal staining, limbal injection, bulbar injection or tarsal conjunctival abnormalities.

8 DISCONTINUATION FROM THE STUDY

Participants may be discontinued at the discretion of the investigator or sponsor in consideration of participant safety or protocol compliance, or at discretion of the participant. Participants discontinued from a study will be reimbursed \$20 per hour for their active involvement in the study (including the initial screening visit). Upon discontinuing, a participant will be offered the option of their data being withdrawn from future statistical analysis. The following is a list of possible reasons for discontinuation from the study:

- Screening failure: Participants will be discontinued if they do not meet the inclusion and exclusion criteria outlined in section 4.2.3.
- Unacceptable performance with products to be used in study: Participants may be discontinued if they are unable to achieve acceptable comfort and /or vision with the study products.
- Positive slit lamp finding: Participants may be permanently discontinued from the study depending on the severity of the condition and on the judgement of the investigator.
- Adverse event: If a participant experiences an adverse event during the study they may be discontinued based on the clinical judgement of the investigator.
- Symptoms: If the participant has persistent symptoms they may be discontinued based on the clinical judgement of the investigator.
- Disinterest, relocation or illness: The participant may choose to discontinue due to reasons within or beyond their control.
- Violation of protocol or non-compliance: The participant will be discontinued if they are unable or unwilling to follow the protocol specified visit schedules and/or study procedures.
- Instillation of topical ocular medication: The participant will be discontinued if they elect to use a topical ocular medication during the study unless that topical ocular medication is prescribed for a limited duration (less than two weeks) to treat a transient condition; in

this case the participant may remain an active participant (at the discretion of the investigator) after stopping topical ocular medication following resolution of the ocular condition).

- Lost to follow-up: The participant will be discontinued if they cannot be contacted and do not return for a final exit visit, and if the investigator has made a reasonable effort to contact the participant for a final study visit.
- Premature termination of the study by the sponsor, CORE or the Office of Research Ethics at the University of Waterloo.

A discontinuation form, stating the reason for discontinuation will be completed, which requires the signatures of both the participant and the investigator except where the participant is lost to follow-up in which case only the signature of the investigator is required.

All discontinuations including their reasons will be included in the final report.

9 STUDY COMPLETION AND REMUNERATION

At the last scheduled protocol visit a study completion form will be completed, which requires the signatures of both the participant and the investigator.

Once their involvement in the study is complete, participants will be informed about receiving feedback following study completion in the Letter of Appreciation.

Participant remuneration will be \$80 for completing the study. In the event that participants withdraw or are discontinued from the study, they will receive \$20 per hour for the time that they were involved in the study.

10 STATISTICAL ANALYSIS AND DATA MANAGEMENT

10.1 STATISTICAL ANALYSIS

All data will be analyzed by CORE at the University of Waterloo on unmasked data using Microsoft Excel and statistical analysis software such as GraphPad and SPSS. Interim data analysis will be conducted after 10 symptomatic and 10 asymptomatic participants have completed the study to determine the optimal time period over which to calculate the slope. The results of the interim data analysis will also be used to calculate the sample size.

Descriptive statistics will be provided on information regarding baseline variables (age, sex, contact lens refractive error distribution, etc.). Data may be evaluated for individual groups

(asymptomatic versus symptomatic) and when both groups are combined. Data will be tested for normality of distribution using Shapiro-Wilk tests. A p -value of < 0.05 will be considered statistically significant. Additional analysis may be conducted.

Table 4 lists the primary outcome variables and anticipated statistical procedures.

Table 4: Outcome variables and anticipated statistical procedures

| Variable | Analysis | Statistical test |
|--------------------------------------------------------------------------------------------------------------------------------------------------------------|--------------------------------------------------------------------------------------------------------------------|--------------------------------------------------------------------------------------------------------------------|
| Tear evaporation rate | Change in relative humidity over time | Slope |
| Tear evaporation rate/Time | Effect of lens type | RMANOVA Mauchly's test of sphericity Greenhouse-Geisser p values Tukey HSD post hoc Paired t -test |
| Tear evaporation rate/ Subjective ratings/Non- invasive breakup time/Lp d ayer thickness (Lp View II - continuous)/Area of the ocular surface | Relationship between tear evaporation rate and subjective comfort and dryness/other tear film assessments | Pearson correlation – r |
| Tear evaporation rate/ Lp d ayer thickness (Tearscope - ordinal)/ Volume of the goggle | Relationship between tear evaporation rate and lpdayer thickness | Spearman correlation – ρ |

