2 OBJECTIVES

The objective of the study is to compare the rate of tear evaporation, measured with a novel evaporimeter, before and after DAILIES TOTAL1 and Biotrue ONEday CLs are worn in symptomatic and asymptomatic contact lens wearers.

The primary outcome variable for this study are the slopes calculated from the change in relative humidity over time.

Other variables of interest include:

- Contact lens dry eye questionnaire-8 (CLDEQ-8) score
- Comfort (subjective rating)
- Dryness (subjective rating)
- Non-invasive break up time
- Lipid layer thickness (Tearscope, LipiView II)
- Ocular surface area (mm²)
- Volume inside the goggle (cm³)

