4.1.2 RANDOMIZATION

A randomization schedule will be generated using a web-based program: (www.randomization.com). Participants will be randomized to the type of contact lens to be worn in each eye at Visit 2. A separate randomization will be generated for symptomatic and asymptomatic participants. The final study randomization schedule will be generated by CORE's Database Administrator, and provided to the research assistants for the study. Study investigators will remain masked to the randomization schedule until the interim data analysis. Study investigators will be granted access to the randomization schedule for the first 10 symptomatic and 10 asymptomatic participants in order to conduct the interim data analysis. Following

calculation of the sample size required to complete the study, study investigators will remain masked to the remainder of the randomization schedule until the study is completed and the database is locked.

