4.5.10 ANTERIOR EYE PHOTOGRAPHS

The participant will be seated at a Zeiss slit lamp attached to a Canon EOS 60D digital camera. A photograph of each eye will be taken at 5x magnification with additional external illumination provided by a Canon Macro Twin Lite flash. The participant will hold a ruler underneath each eye while the photographs are taken. The ruler will serve as a calibration reference when the images are analysed with ImageJ in order to determine the size of the ocular surface in mm². The ruler will be cleaned with an alcohol wipe prior to being given to each participant.

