4.5.16 EVAPORIMETRY

The participant will be seated at an adjustable height table and will place their elbows on the table. The participant will hold a pair of modified swimming goggles (Figures 1A and 1B) over their eyes for 20 seconds while their eyes are open. The participant will be prompted to blink every 3 seconds during the measurement using a metronome (<https://www.youtube.com/watch?v=9ypeNJJeKIs>). The goggle will be removed and ventilated in front of a fan until the relative humidity returns to

baseline levels. The goggle will then be placed over the eyes for 20 seconds while they are closed to measure the evaporation rate from the skin. Three consecutive measurements of open eye and closed eye measurements will be taken. Recordings of the temperature and relative humidity during the measurement will be saved as a text file and images of the temperature and humidity versus time plotted as a graph will be saved as a png file. The rate of tear evaporation will be calculated from slope derived from the change in relative humidity over time. The evaporation rate from the ocular surface will be calculated by subtracting the evaporation rate of closed eye from the evaporation rate of the open eye. The average of three ocular surface evaporation rates will be calculated for each eye.

[figure not shown]

Figure 1: (A) Evaporimeter with arrows showing the location of the temperature/humidity sensors in the swimming goggle. (B) View of the front of the evaporimeter.

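### Nothing requires the primary-outcome slopes to be derived before lens and symptom-group codes are known, and Section 10.1 says that all data are analysed unmasked

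*Combined protocol and SAP*

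**What the plan says.** Section 10.1 makes a general statement with no exception for the primary outcome: "All data will be analyzed by CORE at the University of Waterloo on unmasked data using Microsoft Excel".

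Section 2 defines that outcome: "The primary outcome variable for this study are the slopes calculated from the change in relative humidity over time". Section 4.5.16 gives the route to it. The participant holds the goggle over both eyes for 20 seconds, three open-eye and three closed-eye recordings are made and saved as files, slopes are calculated, and closed-eye rates are subtracted from open-eye rates. Then: "The average of three ocular surface evaporation rates will be calculated for each eye". No rule says when a recording is unusable or what happens to it.

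On lens codes, Section 4.1.2 says: "Study investigators will be granted access to the randomization schedule for the first 10 symptomatic and 10 asymptomatic participants in order to conduct the interim" analysis. After that, "study investigators will remain masked to the remainder of the randomization schedule until the study is completed and the database is locked". Section 10.1 adds that the interim serves "to determine the optimal time period over which to calculate the slope".

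Symptom group is set by the CLDEQ-8 score at Visit 1 (Sections 4.4.2 and 4.5.4). No section describes masking anyone to it.

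**The concern.** Running the final tests with codes attached is ordinary practice. The difficulty is that the plan does not separate testing from derivation. The slope is not a number shown by the device. It is computed from a stored trace of a hand-held goggle, and someone may have to judge whether a trace is usable or where the usable part begins. If that person can see which eye wore which lens, or which group the participant belongs to, those judgements can favour one side without intent.

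The lens-type and symptom-group comparisons are at stake. The study calls itself double-masked, yet Section 4.1.3 concedes that lens markings may reveal the lens to the investigator. Masked derivation would be a useful second safeguard. It matters more because the study is also meant to validate the evaporimeter.

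**Working it through.** **Reading the sections together**

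- *First 20 participants (10 symptomatic, 10 asymptomatic).* Lens codes go to the investigators for the interim. Nothing says their slopes are frozen first, or that these participants are excluded from the final analysis.
- *Later participants.* Lens codes are withheld until lock (Section 4.1.2). Slopes derived before lock would be masked to lens, and slopes derived after it would not. The plan does not say which applies, and Section 10.1 makes no distinction.
- *Symptom group.* No masking is described for any participant.
- *Handling of readings.* The written rule is to average all three. There is no acceptance, repeat or rejection rule.

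**Illustration of size**

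The documents give no SD, effect size or sample size calculation, so there is no stated figure to reproduce. Inputs from the plan are three readings per eye, a paired t-test (Table 4), significance at 0.05 (taken as two-sided), and n = 20 (the minimum target for completers). Assumed inputs are no true lens difference, normal reading noise with SD 1, and favourable handling (loss of the least favourable reading) in 10% or 20% of participants.

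1. The extremes of three standard normal readings have expected values of ±0.846. Losing the lowest leaves a mean of 0.846/2 = 0.423.
2. If a reading is lost separately in each eye, in opposite directions, the eye-to-eye difference moves by 2 × 0.423 = 0.846.
3. The goggle records both eyes at once. If a whole placement is lost, the move is 0.423 × √2 = 0.60.
4. The shift in the mean is the fraction affected times the move. Separate eyes give 0.085 and 0.169. Whole placements give 0.060 and 0.120. All are in single-reading SDs.
5. The standard error with reading noise only is √(2/3)/√20 = 0.183.
6. A normal approximation with that fixed standard error would give 7.5% and 15.3% for separate eyes. This overstates the effect: it uses 1.96 rather than the t value of 2.093 on 19 df, and it ignores the variance that uneven handling adds. Simulating the paired t-test gives:

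| Handling assumed, reading noise only | 10% of participants | 20% of participants |
|---|---|---|
| Separate reading in each eye | 6.4% | 11.3% |
| Whole placement | 5.9% | 8.4% |

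A repeat with 100,000 runs per setting gave 6.1-6.9% and 10.6-12.0% for separate eyes, and 5.7-6.1% and 8.0-8.7% for whole placements. The lower value in each pair fixes the number of affected participants; the higher lets it vary at random.

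7. If the true lens difference also varies between people with an SD equal to one reading SD, the range falls to about 5.4-8%. With half that SD the upper end stays near 10.5%.
8. Losing a reading without regard to lens keeps the error rate at 4.8-5.1%. The harm therefore comes from knowing the code, not from losing a reading.

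No figure was derived for the symptom-group comparison.

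**The case against.** The strongest reply is that the plan already limits the room for judgement. It averages all three rates, so leaving one out would depart from the protocol and would have to be documented (Section 13.4.3). A reader might infer that the plan expects poor traces to be discarded with codes in view. It does not say so, and that inference rests on silence. Nor do the documents say whether the start of a trace is set by hand or automatically.

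Section 4.1.2 also gives real protection. A reader might infer that every participant's slopes are derived with the lens known. For participants after the interim that is not shown, because Section 10.1 can be read as describing only the tests run after lock.

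Two further inferences should be resisted. Ocular area, measured from photographs, may look like a second exposed outcome. The photographs are taken at Visit 1, before lenses are assigned to eyes at Visit 2, and Table 4 uses area only in a correlation, so it cannot move the lens comparison as planned. Nor can one say that bias would push the lens difference in an expected direction: Section 3 gives no direction for DAILIES TOTAL1 against Biotrue ONEday. Only the lens-versus-no-lens and symptom-group hypotheses are directional.

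All of this narrows the point. It leaves the gap in place: no section says that slopes are fixed before codes are merged, and Section 10.1 states the opposite order without exception.

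**Conclusion.** The point holds as a modest one that is cheap to close. The plan permits the primary-outcome slopes to be derived with codes known. That is clearest for lens in the first 20 participants, possible for lens in later ones, and unaddressed for symptom group throughout. The risk is limited to decisions on individual traces that the text leaves open.

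Under the stated assumptions a nominal 5% error rate would be about 6-11% with reading noise only, and about 5.4-8% when the lens difference varies between people by one reading SD. The 10-20% rate of favourable handling and the variance values are assumptions; the documents support none of them. The figures show scale and do not predict what will happen. The interim choice of slope window is a separate, study-wide decision and is not counted in them.

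**What to change.** In Section 10.1, replace the statement about unmasked data with the following order of work:

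- Slopes are derived, and any unusable trace is identified, from files coded only by participant, session and right or left eye. Eye side does not disclose the lens, because lens is randomized to eye. The study ID given at consent is the safer code: separate randomization lists are kept by symptom group, so a randomization ID might reveal the group.
- A trace is rejected only under a rule written in advance that does not depend on the size or sign of the slope. Examples are a starting humidity not at baseline, or an incomplete 20-second recording (fewer than 20 × 4 = 80 samples at the stated rate). Rejecting traces because humidity falls would select on the outcome and should not be used. Otherwise all three readings are averaged.
- The slope dataset is frozen, and lens and symptom-group codes are merged only then for testing. For the first 20 participants the freeze comes before their codes are released at the interim, so the slope window also has to be chosen from the coded traces.

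Reconcile Sections 4.1.2 and 10.1 to match. Session labels still show whether a lens was worn, so this protects the lens-type and symptom-group comparisons but not lens versus no lens.

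The cost is wording and a change in the order of work, with no new visit or measurement. Section 4.5.16 does not say how saved files are labelled, so the labels should be checked for anything that discloses lens or group.

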4.2 STUDY POPULATION

4.2.1 SAMPLE SIZE CALCULATION

Because this is a pilot study, a sample size calculation has not been completed. An interim data analysis will be undertaken after 20 participants (10 symptomatic and 10 asymptomatic) have completed the study. The results of the interim data analysis will be used to calculate a sample size using G*Power.

A p-value of < 0.05 will be considered statistically significant.

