4.2.2 NUMBER OF PARTICIPANTS

Up to 50 participants will be screened using CORE records and advertising approved by the UW Office of Research Ethics. Up to 50 participants will be dispensed/randomized with study products, with a target of at least 10 symptomatic and 10 asymptomatic participants completing the study. Informed consent will be obtained for all participants prior to their enrolment in the study.

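### The time window that defines the primary slope is chosen at an interim with the lens code open and no criterion, and the sample size is set from the same data

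*Combined protocol and SAP*

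**What the plan says.** Section 2 makes the slope primary: "The primary outcome variable for this study are the slopes calculated from the change in relative humidity over time". Section 4.5.16 describes three open-eye and three closed-eye recordings of 20 seconds each, and takes the rate from the slope without giving a start, an end or a fitting rule. The Introduction gives a sampling rate of 4 per second.

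Section 10.1 schedules an interim after 10 symptomatic and 10 asymptomatic completers "to determine the optimal time period over which to calculate the slope". It also says "All data will be analyzed by CORE at the University of Waterloo on unmasked data". For that interim, section 4.1.2 states that "Study investigators will be granted access to the randomization schedule for the first 10 symptomatic and 10 asymptomatic participants". Afterwards, "study investigators will remain masked to the remainder of the randomization schedule until the study is completed and the database is locked".

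On size, section 4.2.1 says "The results of the interim data analysis will be used to calculate a sample size using G*Power", without naming the comparison, target difference, SD or power. Section 4.2.2 sets the ceiling: "Up to 50 participants will be dispensed/randomized with study products". The testing rule is "A p-value of < 0.05 will be considered statistically significant". Section 3 states three hypotheses: lens wear against no lens, one lens type against the other, and symptomatic against asymptomatic wearers. No section says whether the first 20 participants enter the final analysis.

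**The concern.** The primary endpoint is completed part-way through the study, by people who can see which eye wore which lens, under a standard that is never defined. If the size of a lens contrast influences the choice, the window that looks best by chance in the first 20 is carried into a final analysis containing the same 20. The 5% error rate is then no longer protected and the difference tends to be overestimated.

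Keeping the remaining schedule masked does not help, because the outcome definition has already been fixed on open data. A reader of the final report could not tell whether the window was chosen for repeatability, for linearity or for lens separation.

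The sample size raises a lesser version of the same problem. If the observed lens effect goes into G*Power, chance in the first 20 determines how many more are recruited.

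**Working it through.** **The plan's own figures.** There is no N, power, effect size or SD to reproduce. The only stated rate is 0.05, taken here as two-sided.

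**Inputs from the documents.** Interim n = 20 (4.2.1); maximum N = 50 (4.2.2); DT1 in one eye and BOD in the other, so a paired comparison (4.1.1); 20 s × 4 per second = 80 points per recording (4.5.16 and Introduction), so many windows are possible.

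**Inputs assumed.** The number of candidate windows, their correlation, and the shape and noise of the humidity curve. In step 1 the window with the largest interim contrast is kept and the 20 are reused.

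**1. Choosing the window on the lens contrast, with no true lens effect.** With k independent windows, the chance that at least one is significant is 1 − 0.95^k: 14.3% for k = 3 and 40.1% for k = 10. These are upper bounds, since real windows overlap. Simulated paired t-tests gave:

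| Candidate windows | Final N = 20 | Final N = 50 |
|---|---|---|
| One fixed window | about 5% | about 5% |
| 3, equal correlation 0.3 to 0.9 | 8.4-13.8% | 6.7-9.5% |
| 3, saturating humidity curve | 10.4-12.7% | 7.0-9.2% |
| 10, overlapping windows of a 20 s trace | 10-26% | 8-14% |
| 10, equal correlation 0.5 | 29.5% | 14.5% |

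The fourth row pools two trace models. One, with a fluctuating evaporation rate, gave 10-20% and 8-11%. The other, a saturating curve, gave 11-26% and 8-14% over its noise settings.

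**2. Choosing on lens-on versus no-lens.** The same selection on this contrast gave 9-13% (N = 20) and 8-9% (N = 50) with 3 windows, and 15-27% and 10-14% with 10. Closing the lens code does not prevent this, because the visit step itself shows whether a lens is on.

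**3. Choosing without either contrast.** Picking the window with the highest intraclass correlation (ICC) between the two no-lens sets gave error rates, averaged over nine curve and noise settings, of 4.8-5.3% for lens type and 4.8-5.2% for lens on/off. Choosing on the open 20 but testing only the 30 later participants (50 − 20) gave 4.9-5.3%.

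**4. Sample size from the observed lens effect.** For a paired test at 80% power, N ≈ ((1.96 + 0.84)/dz)², where dz is the mean difference over its SD. At dz = 0.5 this is (2.80/0.5)² = 31.4, or 34 with the exact t. An observed 0.5 from 20 people has a 95% interval of 0.03 to 0.96. If dz is truly 0.5, the observed-effect N is 20 or less in 27% of runs and above 50 in 33%. With N held to 20-50 and no true effect, the error is 6.5%, against 5.0-5.7% with an SD from open data and 4.9-5.1% with an SD from closed data.

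**5. Cost of a closed-code SD.** Lens is randomized to eye, so the right-minus-left difference carries the lens effect with a random sign and its variance is about σ²(1 + dz²). At dz = 0.5 the factor is 1.25, and the simulated median N is 41 against 34. At dz = 0.8 the factor is 1.64, and the median is 22 against 15.

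**6. Symptom groups.** At the cap, 25 per group, d ≈ 2.80 × √(2/25) = 0.79 for 80% power, or 0.81 with the exact t. Sizing for lens type does not size this comparison.

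**The case against.** Three points on the other side carry weight.

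- **The harm is conditional.** The study also serves to validate a new device, and linearity or repeatability is a natural reading of the best window. A criterion of that kind, pooled over lenses, would not inflate the error rate. The text establishes a missing criterion and an open code; it does not establish an error rate. This stands, and the figures are illustrations of what the plan leaves possible.
- **The study is called a pilot.** Choosing a window is a proper pilot task, no interim test or early stop is planned, and section 10.1 describes its methods as anticipated. This lowers the stakes without removing the point: the Introduction gives the lens comparison as the purpose, section 3 states hypotheses, and they are tested at 0.05.
- **The code has some use for sizing.** A closed-code SD overstates N, and an open-code SD costs little error (5.0-5.7%). That is a fair argument about sample size. It gives no reason to have the code open while the outcome is being defined.

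The simulations cover only a paired t-test, whereas Table 4 also lists repeated-measures ANOVA with Tukey comparisons. The favourable ICC results are averages over settings, so individual settings vary around them.

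**Conclusion.** The concern holds and should be fixed. The primary slope has no defined window, the rule for choosing it is absent, the lens code is opened for the analysis that makes the choice, the same results set the sample size, and the 20 participants are not excluded from the final tests.

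Confidence is high that the safeguard is missing. How much it matters in practice depends on how the choice would be made. Selection on a contrast could roughly double the nominal 5% at N = 50, and raise it further if the study stops near 20. A choice on pooled repeatability would leave the rate at about 5%. The sample-size element is minor by comparison.

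**What to change.** 1. **Section 10.1.** List the candidate windows. Choose by the ICC between the two Visit 2 no-lens measurement sets of the first 20 completers (section 4.4.3), with lens code and symptom group closed and no lens-on recordings used. Freeze the window before any lens-coded data are opened.
2. **Section 4.1.2.** Delete the investigators' interim access to the schedule.
3. **Section 4.2.1.** State the G*Power inputs: the closed-code SD of the right-minus-left slope difference at Visit 3, a pre-stated target difference, power and sidedness. Say that this sizes the lens-type comparison only.
4. **If the interim stays unmasked.** Label the section 3 tests exploratory and report the contrast for every candidate window. Testing only participants enrolled after the interim would also protect the error rate, but leaves at most 30.

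The cost is a few sentences and no new procedure, since both no-lens sets are already scheduled. There are four drawbacks:

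- An ICC from 20 people is imprecise. It also rewards windows in which people differ from one another, so the chosen window may not be the most precise for a within-person contrast.
- The no-lens recordings are also the comparator for lens wear against no lens. With ICC that test stays balanced (2.3-2.7% in each direction). Choosing by coefficient of variation would tilt it (about 1.7-2.4% in the hypothesised direction, 2.6-3.4% against).
- The closed-code SD overstates N, as shown in step 5.
- The target difference is hard to justify for a new device, and N depends on it. At dz = 0.5, with N held to 20-50, a target of 0.7 times the truth gives 50 in most runs (93% power), and 1.4 times gives 20-31 (62% power).
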